10.5 Appendix 5: Patient Overall Impression of Change

Since the start of the study, my general state of health is:

tick one box only

- [1] Very Much Improved
- [2] Much Improved
- [3] Minimally Improved
- [4] No Change
- [5] Minimally Worse
- [6] Much Worse
- [7] Very Much Worse

10.6 Appendix 6: Medication WHO Drug Dictionary Codes

Name	Code
ESA except darbepoetin alfa	ATC level 4 = B03XA [WHODD drug code = '00909301001', '00928301001', '07973701001', '01703101001']
Darbepoetin alfa	ATC level 4 = B03XA [WHODD drug code = '02198701001']
IV Iron	ATC level 4 = B03AC [WHODD drug code = '00023501001', '90135401001']
RBC transfusion	ATC level 4 = B05AX [WHODD drug code = '01186901001']
Any investigational drug	WHODD drug code = '99999701001'
Hypoxia-inducible factor HIF-PHI	ATC level 4 = B03XA
Iron-chelating agents	ATC code = V03AC01, V03AC02 and V03AC03
Androgens	ATC level 3 = G03B and G03E
Dapsone	ATC level 4 = J04BA
Acetaminophen/paracetamol	ATC level 4 = N02BE, N02AA, R05X

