12 APPENDICES

12.1 Appendix 1: List of Prohibited Concomitant Medication

- Iron-chelating agents (e.g., deferoxamine, deferiprone, or deferasirox therapy) from 4 weeks prior to randomization until EOS visit.
- Androgens from the day of randomization until EOS visit.
- Dapsone in any dose amount from the day of randomization until EOS visit.
- Chronic use of acetaminophen (paracetamol) > 2.0 g/day from the day of randomization until EOS visit.
- Any hypoxia-inducible factor prolyl hydroxylase inhibitor (HIF-PHI) other than roxadustat, as allocated by randomization, until EOS visit.

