5.3 Per Protocol Set (PPS)

The Per-Protocol Set includes all FAS subjects who do not meet any of the reasons to exclude a complete subject from PPS listed in [Table 3](#). This PPS will be used for all disposition, demography and baseline characteristics.

Table 3 Criteria for excluding a subject from PPS

Number	Reasons for exclusion from PPS
1	Subject who receives less than 2 weeks of study treatment.
2	Patient without a valid corresponding Hb. A valid corresponding Hb is defined as an Hb value from the central laboratory that is measured at least 2 weeks after the first dose and was either before the last study drug intake or at maximum three days after the last drug intake.
3	Prescribed study drug compliance during treatment < 75% during the first 24 weeks or until EOT, whatever comes first.
4	Violation of inclusion or exclusion criteria which may affect the assessment of the efficacy of the study drug during the reference period or until EOT, whatever comes first.
5	Subjects where breaking of the randomization code occurs during the reference period or until EOT, whatever comes first.
6	Administration of wrong randomization study drug for more than one week during the reference period or until EOT, whatever comes first
7	Administration of prohibited concomitant medication affecting efficacy listed in Appendix 12.1 of the protocol during the first 24 weeks or until EOT, whatever comes first.
8	Administration of rescue therapy significantly deviating from the protocol during the first 24 weeks or until EOT, whatever comes first.

More information on the derivation of these criteria can be found in the Classification Specifications.

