be selected for the calculation of the average LDL cholesterol of weeks 12-28 (see [Table 33](#) and Section [7.11.4](#) for the analysis windows definition and the differentiation between the MMRM and ANCOVA analyses).

For missing LDL imputation rules, refer to Section [7.11.1](#). Baseline LDL is defined as the LDL value on Day 1. If this value is missing, the latest value prior to first study drug administration will be used.

This analysis will also be repeated for fasted values only as a sensitivity analysis.

6.1.2.3 Use and time to first use of rescue therapy (composite of RBC transfusions, ESA use, and IV iron)

RBC transfusion is collected in the Blood Transfusions form of the eCRF. The use of ESAs and IV iron is collected in the Concomitant Medication form of the eCRF (entries where “Given as Anemia Therapy?” is ticked). These medications will be coded into the ATC and WHO-DRL dictionaries.

The following WHO-DRL codes will be classified as ESA: '00909301001', '00928301001', '02198701001', '07973701001', '01703101001'. The following WHO-DRL code where route is INTRAVENOUS will be classified as IV IRON: '00023501001' and '90135401001'. The following WHO-DRL code will be classified as RBC transfusion: '01186901001'.

Only rescue medication that started during the study treatment and up to the end of Efficacy Emergent Period will be taken into account and considered as use of rescue. Medication started at End of Treatment visit will not be considered rescue for patients completed the treatment. Medication Onset Date is the date of the first use of rescue medication.

For a subject with use of rescue therapy, the time to use of rescue therapy will be calculated (in years) as:

$$(\text{First event date} - \text{Analysis date of first dose intake} + 1) / 365.25$$

With ‘First event date’ defined as ‘Date of first dose of rescue medication’ during the Efficacy Emergent Period and ‘Analysis date of first dose intake’ defined in Section [6.5.4](#)

For a subject without use of rescue therapy, the time to censoring is calculated as:

$$[(\text{Date of End of Efficacy Emergent Period} - \text{Analysis date of first dose intake} + 1) / 365.25$$

With date of End of Efficacy Emergent Period defined in Section [7.11.6](#)

6.1.2.4 Change from BL in SF-36 Vitality (VT) Sub-score to the Average VT Sub-score of Weeks 12 to 28

For details on the calculation of the SF-36 VT scale subscore, see Section [6.1.3.14.1](#)

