$$\frac{\text{Total of IV iron use (mg) from Analysis date of first dose intake to Min(Analysis Date of Week 36 visit, Analysis date of last dose)}}{((\text{Min(Analysis Date of Week 36 visit, Analysis date of last dose)} - \text{Day 1 Date}) + 1) / 28}$$

Monthly is defined as a period of 4 weeks.

Subjects without a relevant concomitant medication record will be assumed that they used no IV iron, thus set to 0 mg.

The same method will be used to calculate monthly IV iron use for week 37-52 and 53-104. Analysis visits will be used as indicated in Section [7.11.4](#)

For subjects with use of IV iron, the time to first use of IV iron is calculated as:

$$(\text{First event date} - \text{Analysis date of first dose intake} + 1) / 365.25$$

With 'First event date' defined as 'Date of first IV iron' during the Efficacy Emergent Period and 'Analysis date of first dose intake' defined in Section [6.5.4](#)

For a subject without use of IV iron, the time to censoring is calculated as:

$$(\text{Date of End of Efficacy Emergent Period} - \text{Analysis date of first dose intake} + 1) / 365.25$$

With date of End of Efficacy Emergent Period defined in Section [7.11.6](#)

6.1.3.10 Occurrence and time to first use of ESA. Number of ESA-Weeks per year

The concomitant medication form of the eCRF in the cumulative visit will be used to detect rescue medication with ESAs as defined in Section [6.1.2.3](#)

The number of ESA-weeks per year are defined as the duration of ESA exposure divided by the total efficacy period in years. Each period when ESA [ATC code = B03XA] was taken will be summed by subjects as follows:

$$[\text{sum (each period (min(End date of efficacy emergent period, End date of ESA therapy) + X days} - \text{Start date of ESA therapy} + 1) / 7)] / \text{total period in years};$$

X will be defined as the duration of the effect of ESA following the last ESA administration, based on the following rules:

- If Frequency = 1 PER WEEK then X=7
- If Frequency = 2 PER WEEK then X=3
- If Frequency = 3 PER WEEK then X=2
- If Frequency = 1 PER MONTH then X=28
- If Frequency = ONCE then X=0
- If Frequency = BIM (Bi-monthly) then X=14
- If Frequency = QD (daily) then X=1

If Frequency = QM (monthly) then X=28
If Frequency = QOD (every other day) then X=2
If Frequency = TID (three times daily) then X=1
If Frequency = 4 TIMES PER WEEK then X=2
If Frequency = EVERY 3 WEEKS then X=21

Additional frequency may be considered depending on the data.

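### SAP Appendix 6 codes prohibited HIF-PHIs by the same ATC class as ESAs, so permitted ESA rescue could be flagged under Per Protocol Set criterion 7

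*SAP*

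**What the plan says.** SAP Appendix 6 lists the dictionary codes for medications of interest. The row "Hypoxia-inducible factor HIF-PHI" is given as ATC level-4 class B03XA, with no drug code. The row "ESA except darbepoetin alfa" has the same class narrowed by four WHO drug codes, and the darbepoetin alfa row has it narrowed by one more.

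Protocol Appendix 1 (section 12.1) prohibits "Any hypoxia-inducible factor prolyl hydroxylase inhibitor (HIF-PHI) other than roxadustat". ESAs are not on that list. Protocol 5.1.3.2 and 5.1.5 allow them as rescue under stated conditions.

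SAP 5.3, Table 3, has two relevant reasons for exclusion from the PPS. Criterion 7 reads "Administration of prohibited concomitant medication affecting efficacy listed in Appendix 12.1 of the protocol during the first 24 weeks or until EOT, whatever comes first". Criterion 8 deals with rescue separately and removes only subjects whose rescue departed significantly from the protocol. For derivation details, SAP 5.3 points to the Classification Specifications, a separate document.

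The SAP also uses two ESA definitions elsewhere. Section 6.1.2.3 identifies rescue ESA by the five drug codes. Section 6.1.3.10 first refers back to that definition, then derives ESA-weeks from the whole class: "Each period when ESA [ATC code = B03XA] was taken will be summed by subjects as follows".

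**The concern.** A rule that identifies a prohibited drug should not also capture a permitted one. With no drug code on the HIF-PHI row, nothing in Appendix 6 separates a HIF-PHI record from an ESA record. If a programmer applies the row to criterion 7 as it stands, every subject with ESA rescue in the first 24 weeks is marked as having taken a prohibited drug and leaves the PPS, whether or not the rescue followed the protocol.

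That would be a post-randomisation exclusion driven by poor response to study drug. The rationale in the protocol's Attachment 1 expects roxadustat to be superior to placebo for rescue use, so the exclusion would probably fall more heavily on placebo. The PPS is the primary analysis set for the two blood-pressure noninferiority comparisons (MAP and time to hypertension), where selective loss of subjects matters most.

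**Working it through.** The plan gives no figure on this point to reproduce. The check is of coding logic, followed by a scale illustration on assumed rates.

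**1. Code overlap.** The inputs are the HIF-PHI rule (class is B03XA) and the five ESA drug codes, all placed in B03XA by Appendix 6.

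- Rule as written: 5 of 5 ESA codes meet the HIF-PHI definition.
- Rule as B03XA minus the five ESA codes: 0 of 5 meet it.

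**2. Link to criterion 7.** The last five rows of Appendix 6 are HIF-PHI, iron chelators, androgens, dapsone and acetaminophen. Protocol Appendix 1 prohibits the same five items. Identifying those drugs is the only evident use of these rows, and criterion 7 is the PPS rule that refers to that list. The link is an inference: criterion 7 does not cite Appendix 6.

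**3. Conflict with criterion 8.** If criterion 7 captured every ESA record in the first 24 weeks, criterion 8 would have no work left to do for ESAs. The two criteria make sense together only if ESA rescue is outside criterion 7.

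**4. Can ESA rescue fall inside the window?** Protocol 5.1.2 allows dose changes from Week 4 and every 4 weeks after that. Protocol 5.1.5 asks for insufficient response to at least two increases in the previous 8 weeks, or to the maximum dose, together with Hb below 8.0 g/dL and a transfusion-risk goal. Two increases can occur at Weeks 4 and 8, so the conditions can be met well before Week 24.

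**5. Scale, on assumed rates only.** Subjects removed = arm size × assumed proportion with ESA rescue by Week 24. Arm sizes are the planned 150 placebo and 300 roxadustat, or 200 and 400 at the upper limit. For example, at 10% and 2%: 150 × 0.10 = 15 and 300 × 0.02 = 6.

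| Assumed ESA use, placebo / roxadustat | Removed at 150 / 300 | Removed at 200 / 400 |
|---|---|---|
| 2% / 2% | 3 / 6 | 4 / 8 |
| 5% / 1% | 7.5 / 3 | 10 / 4 |
| 10% / 2% | 15 / 6 | 20 / 8 |
| 20% / 3% | 30 / 9 | 40 / 12 |

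The percentages are not from the documents. The first row shows that equal rates give no differential loss. The counts also assume that none of these subjects is excluded from the PPS for another reason.

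**6. Which analyses use the PPS.** MAP (SAP Table 22) and time to hypertension (Table 23) use it as the primary set. The EU and US primary endpoints use it only in sensitivity analysis S2 (Tables 12 and 14); their primary analyses use the FAS and All Randomized respectively. SAP Table 16 places MAP and hypertension outside the hierarchical procedure. MAP has an All Randomized sensitivity analysis, and hypertension has All Randomized and FAS analyses.

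**The case against.** The strongest reply is that Appendix 6 may never act alone. Criterion 7 cites the protocol's list, which does not contain ESAs. The operative derivation is in the Classification Specifications, which are not among the documents, and set membership is settled before hard lock after a data review. The acetaminophen row carries no dose limit, although only chronic use above 2.0 g/day is prohibited, which suggests a first screen rather than a final rule. The data needed to separate the drugs exist: five ESA drug codes, and an eCRF tick box marking a medication as anemia treatment.

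All of this stands as a reason for conditional wording. A reader might infer that permitted ESA rescue will certainly be excluded; the documents do not show that. They also do not show that it will not be, and a separate document that may contain a carve-out does not make the SAP row correct. The sponsor has already treated this kind of error as needing a SAP change: the SAP 3.0 revision history updates the iron-chelator ATC codes because the previous ones were wrong.

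A reader might also infer that the summary of prohibited-medication deviations (PD4) would be inflated. That is not supported. SAP 7.2.2 takes deviations from protocol 8.1.6, where they are reported to the sponsor by the investigator or designee, and neither section refers to the code list.

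**Conclusion.** The point holds in conditional form. As written, the HIF-PHI row does not distinguish HIF-PHIs from ESAs. Applied to criterion 7 without a carve-out, it could remove subjects with permitted ESA rescue from the PPS, against the evident intent of criterion 8.

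The size is unknown. Greater loss on placebo is the probable direction, but the protocol's expectation concerns the rescue composite of transfusion, ESA and IV iron, and no ESA rate by arm is given. A reader might go further and infer a quantified shift in the Hb response comparison, or a bias in a given direction for MAP or hypertension. The documents give no basis for either.

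Reach is limited to the PPS analyses. Neither primary analysis changes, S2 of each primary endpoint carries no hypothesis test, and the two comparisons for which the PPS is primary are outside the SAP hierarchy and have analyses on wider sets. This is a wrong stated rule that should be corrected, not a threat to the main results. The conclusion assumes that the HIF-PHI row is used to identify the protocol's prohibited drugs, which is the natural reading of Appendix 6 but is not stated.

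**What to change.** - In SAP Appendix 6, define HIF-PHI by named HIF-PHI drug codes. This is preferable to subtracting the five ESA codes, because the protocol allows any approved ESA, including biosimilars, and the documents do not show that five codes cover them all. The alternative is B03XA excluding every record classified as ESA.
- In SAP Table 3, state that criterion 8 alone governs rescue therapy, so that rescue cannot enter through criterion 7.
- Use the same ESA definition for ESA-weeks (6.1.3.10) as for rescue (6.1.2.3). With the whole class, a HIF-PHI record coded in B03XA would count as ESA time.
- Confirm that the Classification Specifications carry the same definitions.

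The cost is a few lines of SAP text and a matching program check. No new data are needed, and the SAP allows revisions before hard lock.

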10.7 Appendix 7: Inverse probability censoring weighted model

Background

The possible presence of differential SDD rates between the roxadustat arm and the placebo arm, which may indicate informative censoring, will have a strong impact on the use of conventional survival methodology using Cox regression or other non-parametric survival analysis methods, which may lead to heavy bias in the estimation of the hazard ratio (HR). Patients who dropped out may have dependent or nonrandom censoring. The IPCW approach presented below is often used under these situations.

Step 1: Model the censoring mechanism.

In the censoring model, the event of interest is censoring, hence the subjects who are lost to follow-up have an 'event'. Subjects that are not censored, i.e. those who experience the original event of interest, are now considered censored' since their censoring time is not observed. The probability of being censored will be estimated.

Step 2: Estimate the Product-Limit estimator and Cox proportional hazards estimator

Estimate the P-L estimator and Cox regression estimators using time to censoring for each subject j at each time point t , $K_j^0(t)$ and $K_j^Z(t)$. The Cox Model will include e GFR categories (e GFR ≤ 10 , $10 < \text{e GFR} < 15$, $15 \leq \text{e GFR} < 30$, and e GFR ≥ 30), and Dialysis initiation (Yes, No) as time varying covariates. Stratification factors including baseline Hemoglobin values, Study and other common stratification factors will also be included in the model.

Step 3: Calculate the unstablized and stabilized IPCW weights for each of the subjects, j , $W_{\text{unstab}_j}(t) = 1/K_j^Z(t)$, $W_{\text{stab}_j}(t) = K_j^0(t)/K_j^Z(t)$.

Step 4: Estimate the survival and/or Cox model for time to event in the absence of censoring with the IPCW weights, SIPCW.

